12.4.2 Secondary Efficacy Criteria

If a significant difference is found for the main criterion, The secondary criteria will be tested using a hierarchical procedure in the following order:

1. Clinical status as assessed with the seven-category ordinal scale on days 28.
3. Number of days alive free of oxygen.
4. Number of days alive outside hospital during 28 days after randomization.
5. Number of days alive free of intensive-care unit (ICU) admission or mechanical ventilation (invasive or non-invasive) 28 days after randomization.
6. Number of days alive free of mechanical ventilation (invasive or non-invasive) 28 days after randomization.
7. Number of days alive free of ICU admission 28 days after randomization.
8. Rate of all-cause mortality at day 28.
9. Rate of cardiovascular death at day 28.
10. Number of days alive free of acute kidney injury during hospitalization.

Secondary criteria will be compared using Mann-Whitney tests for quantitative variables and ordinal logistic regression to analyze the seven-category ordinal. Chi-square tests for categorical data and Cox survival analysis for time to event. Tests will be performed at a two-sided 5% significant level for one criterion only if a significant difference has been found for the previous criterion in the list.

Differences in medians between groups will be reported with associated 95% CI

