12.3.4 Interim analyses

Interim analyses will be carried out after 33% and 66% of inclusion. They will allow early rejection of the null hypothesis for efficacy. We will use the O'Brien-Fleming spending function to determine the test boundaries. In addition a blinded sample size reassessment procedure will be performed at the second interim analysis that would allow the data safety monitoring board to recommend, if required, an increase of the sample size to reach the expected power.

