12.8 Sample size issues

This trial is designed in a public health emergency context, at which time there is limited information about clinical outcomes in Covid-19 hospitalized patients.

We will include $n=277$ patients in each group to provide the trial with 90% power to detect a difference, at a two-sided global significance level of $\alpha = 0.05$, of 5 days in the median time to clinical improvement between the two groups, assuming that the median time in the standard-care group will be 16 days (B. Cao et al NEJM March 18th 2020). We considered 3 equally spaced analyses allowing early stopping for efficacy according to the O'Brien-Fleming boundaries.

Considering around 25 % of patients in the cardiac insufficiency stratum, we also checked that, in case of significant interaction between stratum and treatment due to a minor effect of the treatment in patients with cardiac insufficiency, this sample size will also allow 80% to detect a 5 days in the median time to clinical improvement in the other stratum that will include $n=207$ patients/group.

Primary efficacy analysis will be on an intention-to-treat basis and included all the patients who had undergone randomization.

The time to clinical improvement will be assessed after day 28, and absence of clinical improvement or death before day 28 will be considered as right-censored at day 28.

The time to clinical improvement will be analyzed by Kaplan-Meier method and compared with a log-rank test.

In addition a blinded sample size reassessment procedure will be performed at the second interim analysis that would allow the data safety monitoring board to recommend, if required, an increase of the sample size to reach the expected power.

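### Secondaries are tested at an unadjusted 5% once the primary crosses at any of three looks; if done on that look's data, the false-benefit rate can pass 2.5%

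*Protocol*

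**What the plan says.** Three parts of the protocol bear on this.

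- **Looks at the primary.** Section 12.3.4: "Interim analyses will be carried out after 33% and 66% of inclusion". Their purpose is stated there: "They will allow early rejection of the null hypothesis for efficacy". The boundary is also stated: "We will use the O'Brien-Fleming spending function to determine the test boundaries". Section 12.8 agrees: "We considered 3 equally spaced analyses allowing early stopping for efficacy according to the O'Brien-Fleming boundaries", with a global two-sided level of 0.05.
- **Gate to the secondaries.** Section 12.4.2: "If a significant difference is found for the main criterion, The secondary criteria will be tested using a hierarchical procedure in the following order". No look is named, so significance at an interim look satisfies the condition.
- **Level for each secondary.** Section 12.4.2: "Tests will be performed at a two-sided 5% significant level for one criterion only if a significant difference has been found" for the preceding criterion. No level by look and no spending function is given for the secondaries, and no sentence holds them back until all patients have completed follow-up.

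The first item in the list is "Clinical status as assessed with the seven-category ordinal scale on days 28". The primary endpoint (section 4.1.1) is time to a two-category gain on that same scale, or discharge alive.

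**The concern.** Testing in a fixed order at full level is valid when there is one analysis. Here the analysis at which the list opens depends on the data. When a secondary is positively correlated with the primary, the primary tends to cross at a moment when the secondary is also high by chance. Testing that secondary at 1.96 at that moment enlarges its benefit tail and shrinks its harm tail. The sum of the two tails can therefore look acceptable while the direction in which claims would be made is above its share.

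At stake are the first claims after the primary. The trial is set up to show superiority of discontinuation (sections 4.2.1 and 12.1), so a false secondary claim would usually be a false claim of benefit. The leading secondaries (day-28 status, oxygen-free days, days outside hospital) measure much the same recovery as the primary, so a positive correlation is plausible.

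**Working it through.** **Inputs from the protocol.** Three equally spaced looks, O'Brien-Fleming, global two-sided 0.05, 90% power (12.8); secondaries at two-sided 5%, so the critical value is 1.96 (12.4.2).

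**Inputs assumed.** The correlation ρ between the primary and secondary statistics, varied from 0 to nearly 1. The secondary has no true effect, and at look k it has the same information fraction as the primary, t = 1/3, 2/3, 1.

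**Step 1. Reproduce the primary's level.** Classical O'Brien-Fleming bounds are 2.004 × √(3/k):
- k = 1: 2.004 × 1.732 = 3.471
- k = 2: 2.004 × 1.225 = 2.454
- k = 3: 2.004

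The O'Brien-Fleming-type spending function gives 3.710, 2.511 and 1.993. Both sets return a two-sided error of 0.0500, so the primary is sound.

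**Step 2. How often the list opens early.** At the effect giving 90% power, the chance of crossing by the second look is 59% (classical) or 56% (spending). Early opening is a main scenario.

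**Step 3. False-benefit rate for the first secondary.** The primary statistic at look k has mean δ√t_k, and its correlation between looks j < k is √(t_j/t_k). The secondary statistic has mean 0, correlation ρ with the primary at the same look, and ρ√(t_j/t_k) with the primary at an earlier look j. Then

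rate = Σ over k = 1 to 3 of P(primary first crosses its upper bound at look k, and secondary Z_k > 1.96).

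This was evaluated by exact multivariate-normal integration. Each cell is classical / spending bounds; the nominal share is 2.5%.

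| ρ | No primary effect | Effect giving 90% power | Maximum over primary effects |
|---|---|---|---|
| 0 | 0.06% / 0.06% | 2.25% / 2.25% | 2.50% / 2.50% |
| 0.3 | 0.25% / 0.25% | 2.66% / 2.64% | 2.72% / 2.72% |
| 0.5 | 0.51% / 0.50% | 2.87% / 2.82% | 2.89% / 2.88% |
| 0.7 | 0.93% / 0.92% | 3.09% / 3.01% | 3.11% / 3.10% |
| 0.9 | 1.67% / 1.64% | 3.48% / 3.40% | 3.48% / 3.47% |
| 0.999 | 2.48% / 2.47% | 3.67% / 3.99% | 4.07% / 4.02% |

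At the 90%-power effect, the rate passes 2.5% once ρ exceeds about 0.17 (classical) or 0.18 (spending).

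**Step 4. Both tails.** At the 90%-power effect with classical bounds:
- ρ = 0.7: benefit 3.09%, harm 0.65%, total 3.74%
- ρ = 0.9: benefit 3.48%, harm 0.10%, total about 3.6%

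Over all primary effects, the total peaks at about 5.0% (classical) or 5.1% (spending).

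**Step 5. The same rate under the remedies.**
- O'Brien-Fleming bounds on the secondary too: maximum 1.1% to 1.6% for ρ from 0 to 0.8, and 2.5% at ρ = 1.
- Pocock-type bound, 2.289 at each look: maximum about 1.9%.
- One test on the complete sample: a false claim requires the final secondary Z to exceed 1.96, which has probability 2.5% whatever the gate does. The rate is therefore at most 2.5%.

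**The case against.** **The timing is not stated.** No sentence says the secondaries are tested on the data at the look where the primary crosses. With one month of enrolment and 28 days of participation (section 5.4), 33% and 66% of inclusion fall at about days 10 and 20 of a 30-day enrolment, when nobody has reached day 28. If a look waits for 28-day follow-up of its cohort (about days 10 + 28 = 38 and 20 + 28 = 48), enrolment is already complete. The natural course is then one test on the full sample, which has no excess. This stands: if recruitment runs to plan, the excess may never arise. It does not remove the point, because the protocol neither requires that course nor excludes testing on partial data, and recruitment may be slower than planned.

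**The promised level is two-sided 5%, and it is essentially met.** This also stands. A reader might infer that the plan breaks its stated level, and the totals in step 4 do not support that. The 2.5% yardstick is a per-direction reading, defensible because the trial claims superiority in one direction.

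**A reader might also infer that false claims of benefit exceed 2.5% in general.** They do not. With no primary effect the rate stays below 2.5% at every correlation, and at the 90%-power effect a correlation above about 0.17 is needed. The protocol gives no correlation. The value near 4% is a limit in which the two statistics are practically the same.

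**The analysis plan may settle it.** Detail on interim levels is often placed there, and that document is not shown. But section 12.4.2 itself fixes the 5% level without qualification, so a plan using another level would depart from the protocol.

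**Conclusion.** The point holds as a conditional one, and it is minor. As written, section 12.4.2 permits unadjusted 5% tests of the secondaries at any of three looks. If they are done on the interim data, with a true primary effect and a positively correlated null secondary, the false-benefit rate is at most about 2.7% to 3.5% for correlations of 0.3 to 0.9, and about 4% in the limit, against 2.5%. The excess is thus 0.2 to 1.0 percentage points over that range. It rests on an assumed correlation and on equal information fractions for the two endpoints. The primary's error rate is unaffected, and the documents do not support a finding that the two-sided 5% level is materially exceeded.

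**What to change.** Add one sentence to section 12.4.2, keeping the order of the list, that adopts one of these:

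1. At the look where the primary is rejected, each secondary is tested against its own group-sequential critical value for that look, for example O'Brien-Fleming or Pocock-type.
2. If all planned patients are already enrolled when the primary is rejected, the secondaries are tested once, at two-sided 5%, on the complete day-28 data.

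The second suits the planned one-month enrolment. The first is needed if the trial can stop with patients still to be recruited.

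The first option costs secondary power after an early stop. At look 1 the critical value would be 3.471 with classical O'Brien-Fleming bounds or 2.289 with a Pocock-type bound, instead of 1.96. A Pocock-type bound loses less at the early looks but more at the final one (2.289 against 2.004). The second option costs only the wait for complete follow-up. Neither changes the sample size or the primary analysis.

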12.5 Safety Analysis

(Serious) adverse events will be tabulated per treatment group.

All (dichotomized) endpoints will be analyzed by chi-square test on proportions and the 95% confidence interval on the odds-ratio will be presented..

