3.2 Secondary objectives

- To evaluate the safety of RAS blockers discontinuation on a composite endpoint of major adverse cardiac events defined as the composite of cardiovascular death, myocardial infarction, stroke or acute heart failure at day 28.
- To evaluate the efficacy of RAS blockers discontinuation:
 1. Clinical status as assessed with the seven-category ordinal scale on day 28.
 2. Number of days alive free of oxygen.

3. Number of days alive outside hospital during 28 days after randomization.
4. Number of days alive free of intensive-care unit (ICU) admission or mechanical ventilation (invasive or non-invasive) 28 days after randomization.
5. Number of days alive free of mechanical ventilation (invasive or non-invasive) 28 days after randomization.
6. Number of days alive free of ICU admission 28 days after randomization.
7. Rate of all-cause mortality at day 28.
8. Rate of cardiovascular death at day 28.
9. Number of days alive free of acute kidney injury during hospitalization.

4 **STUDY DESIGN**

4.1 ***Study endpoints***

4.1.1 **Primary endpoint**

The primary endpoint of the study is the time to clinical improvement from day 0 to day 28, defined as an improvement of two points on a seven-category ordinal scale, or live discharge from the hospital (whichever comes first), as recommended by the WHO R&D Blueprint expert group (3).

The seven-category ordinal scale consisted of the following categories:

1. not hospitalized with resumption of normal activities
2. not hospitalized, but unable to resume normal activities
3. hospitalized, not requiring supplemental oxygen
4. hospitalized, requiring supplemental oxygen
5. hospitalized, requiring nasal high-flow oxygen therapy, noninvasive mechanical ventilation, or both
6. hospitalized, requiring ECMO, invasive mechanical ventilation, or both
7. death.

4.1.2 **Secondary endpoints**

1. **Primary safety endpoint:** major adverse cardiac events defined as the composite of cardiovascular death, myocardial infarction, stroke or acute heart failure at day 28.
2. **Key secondary efficacy endpoints:**
 - Clinical status as assessed with the seven-category ordinal scale on days 28.
 - Number of days alive free of oxygen.
 - Number of days alive outside hospital during 28 days after randomization.
 - Number of days alive free of intensive-care unit (ICU) admission or mechanical ventilation (invasive or non-invasive) 28 days after randomization.

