4.2.4 Randomization

Randomization will be performed with IWRS (Cleanweb).

[figure not shown]
URC Lariboisière Saint-Louis will be done randomization list according to AP-HP Standard Operating Procedures (SOP).

Patients fulfilling the inclusion criteria and without any exclusion criteria that agree to enter the protocol and have signed the inform consent form during the consultation (inclusion) will be randomized in a 1:1 ratio to:

- Group Discontinuation = discontinuation of RAS blocker therapy until the end of the study which correspond to day 28 (experimental arm). After day 28, RAS blockers could be reintroduced or not, according to the physician decision.
or
- Group Continuation = continuation of RAS blocker therapy (control arm)

The randomization will be stratified on the indication of RAS blockers (heart failure vs. other indication).

Inclusion and randomization will be done the same day.

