12 STATISTICAL ASPECTS

12.1 Statistical Design / Model

ACORES-2 will be a phase III national, multicenter, comparative, controlled, randomized, open label trial in parallel groups among patients hospitalized for COVID-19 and treated with RAS blockers. It will test the superiority of the "discontinuation strategy" versus the "continuation strategy". Participants will be distributed in a 1:1 ratio between the 2 groups.

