12.7 Randomisation

The randomisation will be stratified by centre and status of cardiac insufficiency (present/absent).

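### The primary safety endpoint (MACE) is tested by a chi-square that does not use the heart-failure randomisation stratum; a stratified test would be slightly more precise at no cost

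*Protocol*

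**What the plan says.** Protocol section 12.5 sets the safety analysis: "All (dichotomized) endpoints will be analyzed by chi-square test on proportions", reported with a 95% confidence interval for the odds ratio. It mentions no stratum, covariate or significance level.

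The primary safety endpoint is "major adverse cardiac events defined as the composite of cardiovascular death, myocardial infarction, stroke or acute heart failure at day 28" (section 3.2, repeated in 4.1.2).

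Two sections describe the stratification. Section 4.2.4 says "The randomization will be stratified on the indication of RAS blockers (heart failure vs. other indication"), in line with the summary. Section 12.7 says "The randomisation will be stratified by centre and status of cardiac insufficiency (present/absent"). Section 12.8 puts about a quarter of patients in the heart-failure stratum: "Considering around 25 % of patients in the cardiac insufficiency stratum".

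The stratum does enter the efficacy plan. Section 12.4.1 tests the interaction between treatment and strata, and section 12.8 checks power in the stratum without cardiac insufficiency. The safety section has no counterpart.

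**The concern.** Heart-failure status is very likely to predict MACE, because one component of MACE is acute heart failure. Section 2.3 also lists heart-failure admission among the events expected to rise when RAS blockers are stopped. When randomisation balances the arms on a prognostic factor, a test that ignores the factor uses a variance that still contains the between-stratum part. Its standard error is then somewhat too large, and it rejects slightly less often than its nominal level.

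For a harm endpoint, the lost precision makes a real increase slightly harder to see. Section 10.1 treats withdrawal of RAS blockers as the trial's only identified risk and assigns its evaluation to this endpoint, so avoidable imprecision is worth removing. The question is how much there is.

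**Working it through.** **Inputs from the protocol.** 277 patients per arm and about 25% with heart failure (12.8); 1:1 allocation (12.1). This gives 0.25 × 277 ≈ 69 heart-failure and 208 other patients per arm. The protocol states no MACE rate, safety power or margin, so it has no figure to reproduce here. Its 90% power belongs to the efficacy endpoint.

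**Assumptions.** MACE of 5% or 10% in other patients and 10% to 30% in heart-failure patients; a common odds ratio of 1.8; a two-sided 5% level, since 12.5 states none.

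**Step 1: variance.** With stratum shares w and rates p, the share of the crude variance that remains within strata is

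Σ w·p(1−p) ÷ [p̄(1−p̄)], where p̄ = Σ w·p.

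For 5% (other) and 20% (heart failure):
- p̄ = 0.75 × 0.05 + 0.25 × 0.20 = 0.0875.
- Numerator = 0.75 × 0.05 × 0.95 + 0.25 × 0.20 × 0.80 = 0.0756.
- Denominator = 0.0875 × 0.9125 = 0.0798.
- Ratio = 0.947, so the standard error falls by a factor of √0.947 = 0.973, or 2.7%.

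**Step 2: level and power.** Trials were simulated with 69 + 208 patients per arm (one million per scenario). The Pearson chi-square was compared with the Mantel-Haenszel test by heart-failure stratum. Gains are taken before rounding.

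| MACE other / HF | Contrast | Variance ratio | Type I error, crude | Power, crude | Power, stratified | Gain (points) |
|---|---|---|---|---|---|---|
| 5% / 10% | 2× | 0.992 | 4.9% | 46.5% | 46.7% | 0.2 |
| 10% / 20% | 2× | 0.983 | 4.7% | 69.9% | 70.6% | 0.7 |
| 5% / 15% | 3× | 0.973 | 4.7% | 50.6% | 52.0% | 1.4 |
| 10% / 30% | 3× | 0.941 | 4.3% | 71.7% | 74.0% | 2.3 |
| 5% / 20% | 4× | 0.947 | 4.4% | 53.0% | 55.8% | 2.8 |
| 5% / 25% | 5× | 0.917 | 4.0% | 54.1% | 58.5% | 4.3 |
| 5% / 30% | 6× | 0.883 | 3.7% | 54.3% | 60.4% | 6.1 |

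The stratified test held its level (4.9–5.0%) throughout and was never less powerful.

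**Step 3: odds ratio.** Take 5% / 20% and a within-stratum odds ratio of 1.8. The treated rates are 0.0947/1.0947 = 8.65% and 0.45/1.45 = 31.03%. The marginal rates are 0.75 × 8.65% + 0.25 × 31.03% = 14.25% against 8.75%. The crude odds ratio is (0.1425/0.8575) ÷ (0.0875/0.9125) = 1.73. Over the table it runs from 1.66 to 1.79.

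**Step 4: what drives sensitivity.** At a true odds ratio of 2.0, the power of the plain chi-square is 54.5% when MACE is 5% in both strata and 84.8% at 10% / 20% (12.5% overall). That difference of 30.3 points far exceeds any gain from stratifying. Likewise, power for a rise from 10% to 15% is 43%, so 57% of such trials would be non-significant. The 95% half-width is 1.96 × √[(0.15 × 0.85 + 0.10 × 0.90)/277] = 5.5 points. Both figures reflect 277 patients per arm and would barely move with stratification.

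**The case against.** The best defence is that section 12.5 contains no error. A Pearson chi-square after stratified randomisation does not exceed its nominal level. That the test is unstratified is inferred from silence, and an analysis plan could add strata. The gain rests on assumed MACE rates and could be negligible. All of this stands, and it keeps the point minor. It does not remove the point: the section names a method, its plain reading is a crude test and a crude odds ratio, and a better one is available from data already collected.

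A reader might infer four stronger things, none of which the protocol supports.

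- **That the test is insensitive because it ignores the stratum.** Step 4 shows that sensitivity depends mainly on the number of events.
- **That this test is the only safeguard.** Section 12.5 also plans a confidence interval and adverse-event tables by arm. Section 10.3.2.2 requires immediate notification of the most severe cardiac events and stroke, and sends serious-event data to the DSMB before each meeting. Section 6.4.4 allows stopping for an imbalance in serious reactions, and section 10.3.4 sets up the DSMB.
- **That the crude odds ratio is wrong.** It estimates a marginal effect, which is a legitimate intention-to-treat quantity. It lies nearer to 1 because odds ratios are not collapsible.
- **That a non-significant result would be taken as proof of safety.** The protocol does not say so.

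**Conclusion.** The point holds as a minor improvement in precision. Ignoring the heart-failure stratum leaves the MACE test valid, with a type I error of about 3.7% to 5% under the assumed rates. The cost is under one power point at a twofold contrast, 1.4 to 4.3 points at three- to fivefold and about 6 points at sixfold, all at an odds ratio of 1.8. These figures depend on the assumed MACE rates, a common odds ratio across strata and the 25% heart-failure share. If heart failure predicts MACE only weakly, the gain is close to nothing. The limited ability to detect harm that follows from few MACE events would remain.

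**What to change.** First reconcile sections 4.2.4 and 12.7. One stratifies on the indication for the RAS blocker, the other on centre and presence of cardiac insufficiency. These are different variables, and a stratified test cannot be specified until it is clear which was used at randomisation.

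Then state in 12.5 that MACE and the other binary day-28 endpoints are compared by a Cochran-Mantel-Haenszel test on the heart-failure stratum used at randomisation. Report the stratified odds ratio and the stratified risk difference, each with a 95% confidence interval. The day-28 mortality rates fall under the chi-square rule in 12.4.2, so that sentence should match.

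The cost is about a sentence in each section plus the reconciliation. No new data or patients are needed, and no scenario above lost power.
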